9.2 Endpoints

9.2.1 Primary Endpoint

Good or poor performer based on sentence recognition score at 1-month $\geq 90/100$ or $< 90/100$. Good/poor performer status will be compared to pass/fail on the processing parameter tests. (binary classification)

"Fail" status on the processing parameter tests is established as:

- MoCA: score <26/30.
- Stroop test: score below the confidence interval for age 50 years with elementary education, or one or more corrected or non-corrected errors are noted.
- ÉCLA-16+ subtests 3 or 4: one or two scores below normal range, or time taken greater than established confidence intervals.
- Aided thresholds: more than two of five thresholds greater than 30 dB SPL.

The following will be extracted from the CustomSound software database records:

- Datalogging: None-use is defined as less than 2 hours' average time-on-air per day between activation and 1-month (mean -2 standard deviations re. data of Holder et al, 2020).
- AutoNRT: Absent for more than six electrodes. Inability to run AutoNRT or all of the following three NRT tests due to lack of response at maximum comfortable level or non-auditory stimulation leading to termination of the test.
- AGF polarity: For either probe electrode, a slope of negative leading significantly smaller than positive leading, and less than 70% of positive leading.
- Recovery function: For either probe electrode, a relative or absolute recovery period significantly longer than the confidence interval for normal range (Tabibi et al, 2019).
- Spread-of-excitation: For either probe electrode, greater than 35% area under the curve (>5 across the 14-electrode range).

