4.1.2 Bottom-up processing parameters

Bottom-up processing parameters generally relate to auditory sensitivity: both absolute sensitivity to sound, but also discriminating different sounds. Standard aided thresholds for tones presented in a sound field are used to test access to sounds of sufficiently low levels. Elevated thresholds are potentially caused by loss of sensitivity in any part of the CI sound processor function, but also insufficient stimulation current levels. However, current levels may be required to be substantially higher in cases of poorly positioned electrode arrays or very poor neural survival in the auditory nerve. Current levels that would produce aided thresholds in an acceptable range may not be obtained either because of device limitations or due to producing side-effects, such as facial nerve stimulation. Non-optimal electrode position may be unavoidable due to abnormal cochlear structure or morphology (either congenital or developed etiologies). Patchy or overall poor neural survival may be similarly present in these cases. We note that normal ranges for current levels (maps) used in CI processors are large (for example, larger than the typical individual dynamic ranges) and there is to date no evidence in the literature that lower or higher standard monopolar current levels are associated with poor speech recognition (excepting extreme cases). Therefore, only aided thresholds are directly pertinent to measuring sensitivity to sound.

Discriminating different sounds, once they are coded by the CI sound processor, relies on both temporal and spectral discrimination. Auditory nerve responses to the biphasic current pulses produced by the CI are highly synchronized (e.g. Tabibi et al, 2019). The compound action potential

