(CAP) produced by neuronal responses elicited by a monopolar biphasic current pulse applied to a given electrode contact may be recorded using adjacent electrode contacts. The average amplitude of the resulting waveform, after removing artifacts via a forward-masking method, can be characterized by the N1-P2 amplitude. Nucleus devices use a standard measurement algorithm to determine the threshold for neural response (Auto-NRT) in terms of current level across all 22 electrode contacts. As for subjective stimulation current levels, as described above, Auto-NRT levels have a wide normal range, and absolute levels do not appear to be associated with performance outcomes with CI. However, CAP threshold levels are required to investigate supra-threshold behaviour.

From the Auto-NRT response threshold for any given electrode contact, the recruitment of neural responses with increasing current level may be inferred via the CAP amplitude growth function (AGF). Monopolar biphasic pulses used in all standard testing and sound processing are of leading-negative, following-positive polarity. However, peripheral dendrites are more sensitive to negative phases compared with positive phases. Leading phases generally have a greater stimulating effect due to the partial cancelling of the following-phase electric field by the leading phase. Therefore, more rapid growth in CAP amplitudes for leading-positive (anodic) pulses than for leading-negative (cathodic) pulses is indicative of poorer survival of peripheral axons (Hughes et al, 2018).

Refined measurement of the processing parameters of the cochlear nerve via electrically evoked CAP requires sufficient baseline amplitude in order to observe the effects of detuning the optimal stimulation parameters. Mapping out the AGF allows one to determine a baseline stimulation current level (CL) to obtain sufficient baseline wave amplitude (using standard leading negative phase). The effect of increasing the masker-probe interval on the CAP amplitude maps out the recovery function of the auditory nerve (Tabibi et al, 2019). Departures from the normal function, such as excessive absolute or relative refractory periods could indicate poor neural survival, but in any case low growth of amplitude with masker-probe interval would also indicate low effectiveness of stimulation pulses, such that the sound amplitude variations coded by the sound processor would be poorly represented at the neural level.

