7.2.3 Number of Subjects Required

For a test battery that has an underlying moderate specificity and sensitivity of ~80%, a total of 30 subjects should be sufficient to conclude that there is a relationship between pass/fail outcome of the battery (cumulatively – fail on any test -> fail) and good/poor performance based on sentence test score criterion. Therefore, we aim to recruit 30 or more subjects.

The sample size calculation is to be found in section 9.3.1.

All patients implanted since the centre started using their specific test battery will be screened for eligibility. The centre's staff currently estimate that 30 or more patients are eligible.

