7.2.7.1 Blinding Procedures

Not applicable.

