7.3.3.4 ECAP-based bottom-up tests (post-surgery)

Specific ECAP-based standard tests of bottom-up processing were established at the centre. Firstly, automatic ECAP thresholds using "AutoNRT" are measured for each intracochlear electrode using default parameters. Then one basal electrode (number 8) and one apical electrode (16) is used for subsequent tests. If there is no AutoNRT response on one of these electrodes, then an adjacent one

is used. All subsequent ECAP testing uses the forward masking artifact reduction technique with equal masker and probe levels.

Firstly, a negative-leading AGF is measured up until 220 CL or the subject indicates that the sound is too loud. Then an AGF is measured using the positive-leading polarity pulses.

The CL to obtain 100 μ V is determined from the standard AGF, or the maximum tolerable CL if 100 μ V was not obtained. This CL is used for subsequent recovery function and SOE tests.

Recovery functions are obtained using a standard sequence of masker-probe intervals and the CustomSound EP software computes the absolute and relative refractory periods.

SOE functions are obtained using a specific sequence of maskers so reduce overall test time. The maskers span 14 electrode locations but not all locations are used. The CustomSound EP software computes the 50% maximum amplitude width (in electrodes). The area under the curve can be computed manually (up to 14 electrode units).

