9.4 Sample Size Determination

Two scenarios with different underlying good/poor performer proportions were simulated (see figures 3 and 4): 50/50 and 40/60. $\geq 80\%$ power is obtained under both scenarios. Higher specificity and sensitivity would increase the power. Increasing the total number of subjects would also increase power.

[figure not shown]

Figure 4: Power calculations for a 40%/60% good/poor performer scenario.

Based on sample size calculations, a total of 30 eligible subjects are required to provide $>80\%$ power to reject the null hypothesis for the statistical test for the primary objective.

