14 DATA MANAGEMENT

The CRF will capture the datapoints necessary to determine the subject status according to the criteria described in section 7.2.5.

Source data will be captured in clinic notes, paper-based source data worksheets, or printed directly from testing software. If electronic medical records do not permit read only access for monitoring purposes, a certified printout must be provided. ECAP measurements made using CustomSound EP will be processed by the sponsor. The anonymised CustomSound database records (CDX files) will be provided to the sponsor via upload to the data capture portal.

Data collection will be performed using [REDACTED] for electronic data capture (EDC) on electronic Case Report Forms (eCRFs). Site staff will be trained on the completion of the eCRFs prior to obtaining access to the system and will have their own Login/Password. Access to clinical study information will be based on an individual's role and responsibilities.

[REDACTED] uses role-based user permissions for data entry, viewing, and reporting options. All communications between users and the EDC server are encrypted. Web servers are protected by a managed firewall. This application is designed to be in compliance with applicable regulations including 21 CFR Part 11.

The application will include programmed data consistency checks and supports manual generation of data clarifications/queries, including documentation of site responses. The application maintains a

comprehensive audit trail for all data entered, including updates and queries, and documents the time that each entry occurred and who made the entry.

Principal Investigators will affirm that the data for each subject at their site is accurate and complete by way of an electronic signature.

In addition, de-identified electronically generated data will be collected from CustomSound clinical fitting software and electrophysiology software. The unamended data file shall be regarded as the source.

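### Does the loosely worded rule for NRT tests that could not be run leave the battery's pass/fail class, and so the primary test, undefined?

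*Combined protocol and SAP*

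**What the plan says.** Section 7.2.3 makes the battery cumulative ("cumulatively – fail on any test -> fail"). Section 9.2.1 lists what counts as a fail on each test. Its only provision for a test that could not be carried out sits in the AutoNRT item: "Inability to run AutoNRT or all of the following three NRT tests due to lack of response at maximum comfortable level", or because non-auditory stimulation ended the test. The three tests that follow (AGF polarity, recovery function, spread of excitation) define a fail from a measured result.

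Section 7.3.3.4 gives the order of testing. The AGF comes first and yields the current level for 100 µV, or the maximum tolerable level if 100 µV is not reached; "This CL is used for subsequent recovery function and SOE tests". If a probe electrode has no AutoNRT response, a neighbouring one is used. Section 4.1.2 notes that refined ECAP measurement "requires sufficient baseline amplitude in order to observe the effects of detuning the optimal stimulation parameters", and that the current levels needed for acceptable aided thresholds may be unobtainable because of device limits "or due to producing side-effects, such as facial nerve stimulation".

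Section 9.4 claims more than 80% power with 30 subjects and adds that "Higher specificity and sensitivity would increase the power".

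A side point concerns the outcome. Section 7.1 recruits subjects who have primary endpoint data, while section 9.1 gives as an example that a missing score at 1 day or 1 month might be taken as zero.

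**The concern.** The fail status of the battery is one side of the primary two-by-two table. If a subject's class depends on how one phrase is read, the variable is not fully fixed. The affected subjects may not be a random subset either: section 4.1.2 ties a need for high current to poor electrode position or poor neural survival, which are among the limiting factors under study. If such subjects are poor performers and are counted as passes, sensitivity and power fall.

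The choice could also be made with the outcome in view. Section 14 states that "ECAP measurements made using CustomSound EP will be processed by the sponsor", and section 7.2.7.1, headed "Blinding Procedures", is marked not applicable. Taking whichever reading gives the smaller p-value would raise the type I error. The assumed zero looked like a second loose end, because a zero places the subject among the poor performers.

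**Working it through.** **Inputs.** n = 30; sensitivity and specificity about 80% (7.2.3); good/poor split 50/50 or 40/60 (9.4), so 15/15 or 12/18; two-sided α = 0.05, chi-squared, or Fisher where cell numbers are insufficient (9.3.1). The documents give no not-run rate, so every count of affected subjects below is an assumption.

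**Step 1: the plan's own figure.** Let a of n1 good and b of n2 poor performers fail, with T = a + b. Chi-squared rejects when 30·[a(n2−b) − b(n1−a)]² / [n1·n2·T·(30−T)] > 3.841. Power is the sum of Bin(a; n1, 0.2)·Bin(b; n2, 0.8) over rejecting tables. Chi-squared (Fisher): 93.9% (88.5%) at 12/18 and 94.1% (87.2%) at 15/15. The claim of more than 80% holds.

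**Step 2: 80% sensitivity taken to include the open class as fails.** Let k poor performers be in the open class. The others fail with probability (0.8·n2 − k)/(n2 − k); for k = 2 and n2 = 18 this is (14.4 − 2)/16 = 0.775. If the open class is then counted as pass:

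| k | 12/18 | 15/15 |
|---|---|---|
| 1 | 88.2% (79.6%) | 87.6% (76.4%) |
| 2 | 79.4% (68.0%) | 77.4% (61.3%) |
| 3 | 67.7% (55.1%) | 63.7% (44.0%) |

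Counted as fail, power stays at 94–95% (87–89%).

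**Step 3: 80% sensitivity taken to include the open class as passes.** The others now fail with probability 0.8·n2/(n2 − k); for k = 2 and n2 = 18 this is 14.4/16 = 0.90. Counted as pass, chi-squared power for k = 1 to 3 is 94.8–97.1% at 12/18 and 95.2–98.2% at 15/15, and it is higher still if the class is counted as fail. The loss in step 2 therefore comes from where the 80% is anchored, which the documents do not say.

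**Step 4: good performers affected too.** Start from 80/80 with the open class as pass. Let a share f of the subjects who would otherwise pass be in it, equally in both groups, and count them as fail. Specificity becomes 0.8(1 − f) and sensitivity 1 − 0.2(1 − f). At f = 0.1 these are 0.72 and 0.82, and power is 88% (81%) at 12/18 and 88% (77%) at 15/15. At f = 0.2 it is 80% (73%) and 80% (65%). If only good performers are affected, f = 0.2 gives 71% (61%) at 12/18. Here the wider reading of the rule lowers power, the reverse of step 2.

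**Step 5: type I error.** Take 12/18, a recorded-fail probability of 0.40 or 0.56 and an open-class probability of 5%, 10% or 15%, the same in both groups. With either reading fixed, the error is 4.9–5.0% (Fisher 2.3–3.0%). If the better of the two readings is taken after the data are seen, it is 6.8%, 7.6–7.7% and 8.1–8.2% (Fisher 3.6–3.7%, 4.0–4.4%, 4.4–4.7%).

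**Step 6: one table near expectation.** With 2/12 good and 14/18 poor performers failing, moving 2, 4 or 5 poor performers to pass gives p = 0.007, 0.033 and 0.063 (Fisher 0.011, 0.058, 0.121).

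**Step 7: the assumed zero.** Adding one zero-filled subject takes 2/12 v 10/17 to 2/12 v 11/18, p = 0.023 to 0.016 (Fisher 0.053 to 0.026). It takes 3/12 v 12/17 to 3/12 v 12/18, p = 0.016 to 0.025 (Fisher 0.025 to 0.060). Chi-squared does not cross 0.05 in either example; Fisher does, once in each direction.

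**The case for a change.** The strongest case for a change is that this is the definition of a primary variable, that no other section settles the phrase, that both readings can hurt depending on who is affected, and that a sentence would fix it. Section 9.3.1 sets a formal test at 0.05, so the feasibility label does not excuse looseness. Section 9.3.1 also does not define insufficient cell numbers. The expected off-diagonal cells at 12/18 are only 0.2 × 12 = 2.4 and 0.2 × 18 = 3.6, so Fisher may well be used, and under Fisher one affected poor performer is enough in step 2 (79.6%; 76.4% at 15/15).

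The ambiguity stands, and so does the inflation under chi-squared if the reading is picked after the results are known. The rest is weaker. Fisher, which makes the step 2 loss larger, also keeps even the picked-reading error below 5%. The case is rarer than it first looks: section 7.3.3.4 allows a neighbouring electrode, and it runs the later tests at the maximum tolerable level when 100 µV is not reached, so low amplitude alone does not stop them. The subject must also have no fail on any other item, including absent AutoNRT on more than six electrodes. The facial-nerve remark in section 4.1.2 concerns levels for aided thresholds, not ECAP runs. The same section reports no clear link between absolute AutoNRT or current levels and performance, extreme cases apart, so clustering in poor performers is plausible but not established.

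**Conclusion.** No change to the plan follows. The rule can be read two ways, but this is missing detail of a kind that an analyst settles once, when deriving the battery variable, and applies to everyone. Either reading used consistently gives a valid test, with type I error of about 5% under chi-squared and less under Fisher. The plan's power claim reproduces at 87% to 94% across both splits and both tests.

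A shortfall below 80% under chi-squared needs assumptions that the documents do not supply. In step 2 these are that the 80% sensitivity counts the open class as fails, that at least two poor performers are in it, and that they are then counted as passes. In step 4 they are that good performers are affected in sufficient numbers and that the class is counted as fail. With one affected subject in step 2, chi-squared power is still about 88%. The direction is unknown, so the figures do not favour either reading. The inflation to 6.8–8.2% describes choosing the reading after seeing the results under chi-squared; it is not a property of either reading.

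The assumed zero is a matter of wording. Section 7.3.3.6 attaches verification of a zero to the noise conditions only, and section 9.1 itself notes that levels are often omitted at floor or ceiling, so its example may concern noise scores. A subject truly at floor is below 90 whatever value is entered.

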9.2.2 Secondary Endpoints

There are no secondary endpoints.

9.2.3 Exploratory Endpoints

- Sentence recognition score at 1-day in quiet.
- SSQ12 score at time of inclusion.
- Sentence recognition score at 1-month: In quiet and in fixed levels of babble 10 dB & 5 dB SNR, and SNR50.
- Score/s at 1-day, 1-month, and later time points post activation up until the time of recruitment for various fixed SNRs.

9.3 Hypotheses

9.3.1 Primary Hypothesis

The primary objective is to confirm a selection of testable patient-related and device-related processing parameters that limit performance between 1-day and 1-month post-activation in adult CI users. Therefore, we will test the association between being good/poor performer and the outcome of the centre's test battery. A contingency table between the performer status and processing test result can be generated (Figure 3, top left):

[figure not shown]

Figure 3: Sample size calculation with contingency table (upper left).

H1: The primary hypothesis is that there is a significant relationship between the good/poor classification and the test battery pass/fail.

H0: The alternative to the primary hypothesis is that there is no significant relationship.

A chi-squared test (at alpha=0.05, so p<0.05) can be used to test this hypothesis. If insufficient numbers are found in a single cell, a Fisher's exact test can be used instead.

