9.6 Primary Endpoint Analyses

The contingency table between good/poor performer and pass/fail of processing tests will be analysed using a chi-squared or Fischer's exact tests.

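### The primary test is chosen after the table is seen, on an undefined small-cell trigger; one pre-named exact test would remove the ambiguity and gain about 1 to 5 points of power at n=30

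*Combined protocol and SAP*

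**What the plan says.** Section 9.3.1 frames the primary hypothesis without direction: "there is a significant relationship between the good/poor classification and the test battery pass/fail". On the test it says "A chi-squared test (at alpha=0.05, so p<0.05) can be used to test this hypothesis", and it then allows Fisher's exact test as a substitute on this condition: "If insufficient numbers are found in a single cell". Section 9.6 keeps both options: the contingency table "will be analysed using a chi-squared or Fischer's exact tests".

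Neither section says how small a cell must be, whether the count is observed or expected, whether the chi-squared test carries a continuity correction, or whether the test is two-sided.

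Section 9.4 says of the 50/50 and 40/60 good/poor splits that at least 80% "power is obtained under both scenarios". It concludes that "a total of 30 eligible subjects are required to provide" more than 80% power. The test behind that figure is not named in the text, and Figures 3 and 4 are not reproduced in the copy reviewed. Section 7.2.3 gives the effect size (sensitivity and specificity of about 80%) and the rule that failing any one test fails the battery.

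**The concern.** The study has one primary test, and the plan lets the analyst settle which one after seeing the counts. In a table of 30 subjects, small cells are what a working battery produces. At a 50/50 split and 80% accuracy, each misclassified cell averages 15 x 0.2 = 3 subjects.

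The trigger will therefore often be in question, and the two tests are not interchangeable at this size. Fisher's test is conservative and the uncorrected chi-squared test sits close to 5%. The choice can decide whether the study reports an association, and the power of the primary analysis cannot be stated until the trigger is defined.

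**Working it through.** **Inputs.** N = 30, only the total fixed (9.4). Sensitivity = specificity = 0.80 (7.2.3). Proportion of good performers g = 0.50 and 0.40 (9.4). Section 4.2.2 expects 30-50% good performers and reports 16/61 = 26% in a consecutive series, so g = 0.30 and 0.26 serve as a sensitivity check. Alpha = 0.05 (9.3.1). Two-sided testing is an assumption, taken from the non-directional hypothesis.

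**Method.** Exact enumeration of all 2x2 tables with N = 30. The cell probabilities are:
- poor and fail: 0.8(1-g)
- poor and pass: 0.2(1-g)
- good and fail: 0.2g
- good and pass: 0.8g

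Each table's weight is its multinomial probability. Power is the total weight of tables with p < 0.05. Size is the same sum with independent margins, using the battery fail rate f = 0.8(1-g) + 0.2g, which is 0.50 at g = 0.50 and 0.56 at g = 0.40. Boschloo's test orders tables by the two-sided Fisher p-value, maximises the tail probability over the common fail rate for each good/poor split, and is then averaged over splits.

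**Step 1: the plan's own figure.** At 50/50 and 40/60, uncorrected chi-squared has power 93.7% and 92.9%, Yates-corrected chi-squared 87.1% and 85.5%, and Fisher 88.8% and 88.2%. The claim of at least 80% holds for each.

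**Step 2: does the choice matter?** Chi-squared is significant and Fisher is not in 5.0% (50/50) and 4.8% (40/60) of data sets. The reverse occurs in no table with N = 30. One example:

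| | Fail | Pass |
|---|---|---|
| Poor | 11 | 4 |
| Good | 5 | 10 |

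- Chi-squared = 30 x (11x10 - 4x5)^2 / (15 x 15 x 16 x 14) = 243,000 / 50,400 = 4.82, p = 0.028.
- Fisher, upper tail = (4,099,095 + 621,075 + 47,775 + 1,575 + 15) / 145,422,675 = 0.0328. The row totals are equal, so two-sided p = 2 x 0.0328 = 0.066.
- The smallest observed cell is 4. The smallest expected cell is 15 x 14 / 30 = 7.

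An observed-below-5 trigger sends this table to Fisher (not significant). An expected-below-5 trigger keeps chi-squared (significant).

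**Step 3: the procedure under each reading of the trigger** (each pair is 50/50, then 40/60):

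| | Observed cell <5 | Expected cell <5 | Boschloo throughout |
|---|---|---|---|
| Fisher used, planned effect true | 97.8%, 98.3% | 28.1%, 48.7% | n/a |
| Fisher used, no association | 37%, 56% | 29%, 53% | n/a |
| Size | 2.5%, 2.7% | 4.0%, 3.8% | 4.5%, 4.4% |
| Power | 88.8%, 88.2% | 92.7%, 91.1% | 93.4%, 92.1% |

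Under the observed-count reading, size and power equal those of Fisher alone to four decimals.

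**Step 4: gain from Boschloo's test.**
- Over the observed-count reading: 93.35 - 88.76 = 4.6 points and 92.11 - 88.16 = 4.0 points.
- Over the expected-count reading: 93.35 - 92.69 = 0.7 points and 92.11 - 91.11 = 1.0 point.

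**Step 5: fewer good performers.** At 30% and 26% good performers, with 80% accuracy kept, even the expected-count rule goes to Fisher in 84% and 92% of data sets. Its power is 85.9% and 82.5%, against 88.1% and 85.5% for Boschloo, a gain of 2.2 and 3.1 points.

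**The case against.** Chi-squared with a Fisher fallback is conventional and valid, and this is a single-centre, non-interventional feasibility study. Alpha is an upper limit, so a size of 2.5-4% respects it. The power target is met with about 8 points to spare under the less powerful reading of the trigger. Section 7.2.3 treats 30 as a minimum, so a few more subjects could recover the same power. All of this stands, and it keeps the point minor.

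Three stronger readings are tempting, and the documents do not support them.

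- **Fisher will nearly always be used, at about half the nominal alpha, for a loss of 4-5 points.** This needs the trigger to be an observed count below 5 and, for the 98% figure, the planned effect to be true. The plan gives no threshold. Its wording about numbers found in a cell allows an observed-count reading, but the customary criterion for the chi-squared approximation is the expected count. On that criterion Fisher is used in 28% or 49% of data sets and the gain is 0.7-1.0 points.
- **Choosing after the fact inflates the error rate.** Fisher never rejects at N = 30 where uncorrected chi-squared does not, so always taking the more favourable result equals using chi-squared throughout. Its size is 4.8% and 5.0% in the two planned scenarios.
- **The power statement in 9.4 is wrong.** It holds for every variant computed.

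**Conclusion.** The point holds as a pre-specification and efficiency improvement, not as an error in a stated figure. Sections 9.3.1 and 9.6 leave the sole primary test to a trigger that nobody could apply unambiguously. In about one data set in 20 the choice between the two tests would decide the result. Depending on the reading, the same sentence gives power of 88.8% or 92.7% at a 50/50 split, with size 2.5% or 4.0%.

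A single unconditional exact test gains about 1 to 5 points in the planned scenarios. These figures assume two-sided testing, N = 30, the plan's 80% accuracy, uncorrected chi-squared, and 5 as the cut-off on either reading. If accuracy were 75%, an assumption outside the plan, Fisher would have 70-71% power and Boschloo 78-80%, so the choice would matter more.

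**What to change.** In 9.3.1 and 9.6, replace the data-dependent choice with one pre-specified test at two-sided 0.05. Boschloo's unconditional exact test, conditioning on the numbers of good and poor performers, is preferred. It keeps size below 5%, rejects every N = 30 table that Fisher rejects, and had more power than either reading of the current rule in all four splits computed. Uncorrected chi-squared throughout has slightly more power, but its size reaches 5.1% at 30% good performers.

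In 9.4, name the test and quote its power (93.4% at 50/50 and 92.1% at 40/60 for Boschloo). If the sponsor prefers Fisher, naming it alone also settles the ambiguity, at 88.8% and 88.2% power.

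The cost is one sentence in the plan and a restated power figure. No extra subjects or data are needed, and the test is available in standard software. The downside is a test name less familiar to readers.
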